- To assess feasibility of the simultaneous insertion of coated and uncoated ETT, CVC and UC in recently admitted critically ill patients without previous invasive devices in a randomized controlled trial.
- To determine how many patients admitted to the ICU will require CVC, ET and UC insertion and, of those, how many will develop sepsis from 48 hours after randomization until day 28 after randomization or until ICU discharge.

Secondary objectives (clinical outcomes):

- Occurrence of nosocomial sepsis up to 28 days after randomization in control (uncoated devices) versus intervention (coated devices) groups
- Combined endpoint of any of the following infections occurring during ICU stay: Ventilator associated pneumonia (VAP), Catheter related bloodstream infection (CRBSI) and Catheter associated urinary tract infection (CAUTI).
- Occurrence of each nosocomial infection individually (VAP, CRBSI, CAUTI) in both groups and rates of positives cultures at each site.
- ICU and Hospital mortality in both groups.

3. Study methods

The full methods section, including detailed intervention and eligibility (inclusion and exclusion criteria), is explained in the Protocol.

3.1) Trial design

Pilot exploratory, randomized, open label, controlled trial. Critically ill patients which will demand placement of invasive devices for organ support (endotracheal tube, central venous catheter and urinary Foley catheter) will be randomized 1:1 to receive coated (Bactiguard®) or habitual (non-coated) devices.

3.2) Method of randomization and concealment allocation

Randomization list will be electronic generated using appropriate software and will be done in blocks stratified by site and by the presence of sepsis at randomization. Allocation group will only be informed after patient register in the electronic database, thereby preventing the investigator of anticipating for which group the patient will be randomized. Due to technical reasons, there will be no blinding.

3.3) Outcomes

The analysis of the two main outcomes involves both the feasibility of the study and the need to obtain epidemiological data on the occurrence of nosocomial sepsis after ICU admission. The feasibility will be assessed by study recruitment rate and by local input on the challenges of the randomization process. We expect a recruitment rate of approximately 1.3 patients a month per site.

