Sepsis will be defined as the occurrence of infection plus presence of organ failure, assessed by the Sequential Organ Failure Assessment (SOFA) score (Singer, JAMA 2016; Vincent, Intensive Care Med 1996). The presence of infection with an increase in SOFA score in at least two points will be considered as sepsis (Singer,

JAMA 2016). Sepsis will be further classified as probably related to devices or non-related to the devices after adjudication. Sepsis non-related to the devices will be those where an obvious source of infection that is not related to the devices and is present at device insertion or when the time between device insertion and sepsis diagnosis is less than 48 hours. Obvious sepsis sources unrelated to the devices include: Meningitis, soft tissue infections away from the puncture site (i.e., necrotizing fasciitis), intrabdominal infection and surgical wound infection. An introduction of a new antibiotic class will be used to trigger investigation.

VAP will be defined considering the classic diagnostic criteria (Kalanuria, Crit Care 2014):

1. New or progressive radiographic consolidation or infiltrate. In addition, at least 2 of the following:
 - a. Temperature $> 38^{\circ}\text{C}$
 - b. Leukocytosis (white blood cell count $\geq 12,000 \text{ cells/mm}^3$) or leukopenia (white blood cell count $< 4,000 \text{ cells/mm}^3$)
 - c. Presence of purulent secretions

CRBSI will be defined if **one** of the following is present plus criteria for identifying the catheter as the source (ECDC, 2013):

1. Patient has a recognized pathogen cultured from one or more blood cultures, and the pathogen is not related to an infection at another site.

OR

2. Patient has at least one of the following signs or symptoms: fever ($>38.0^{\circ}\text{C}$), chills, or hypotension, and the pathogen is not related to an infection at another site or, if the organism is a common commensal, it must be present from two or more blood cultures drawn on separate occasions. **AND**

3. Culture of the same organism from both the catheter tip and at least one percutaneous blood culture
4. Culture of the same organism from at least two blood samples (one from a catheter hub and the other from a peripheral vein or second lumen) meeting criteria for quantitative blood cultures (at least 5 times greater in

7(13)

catheter blood) or differential time to positivity (at least 2 hours earlier in catheter blood).

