Therefore, for CRBSI to be diagnosed, patient must have criteria 1 OR 2 plus 3 OR 4.

Finally, CAUTI will be defined if **all** the following are present (Nicolle, Antimicrob Resist Infect Control 2014):

1. One or more organisms are present at quantitative counts $\geq 10^5$ colony-forming units/mL from an appropriately collected urine specimen
2. The attending physician believes there is an acute infection and prescribes antibiotics
3. There is no other plausible source of infection at the time the diagnosis of CAUTI is made

The number of antibiotic free days at 28 days will be defined as 28 less the number of days the patient received antibiotics.

All events will be adjudicated by the coordinating center.

3.4) Sample size

This is a pilot study including 100 unique patients. The density of incidence of sepsis and other device-related infection (VAP, CRBSI and CAUTI) will be calculated as the number of events over the total number of patients/day at risk. For the primary outcome of incidence of sepsis, this sample size will be able to inform 95% credible intervals with approximately 3 events per 100 patient-days overall (4 events per patient-day per group), and interval length based on Bayesian *Poisson* regression model with intercept parameter assuming non-informative normal prior centered in 8 event per 100 patient-days incidence rate, $N(e^{0.08}, 5)$.

The prior has a very large standard deviation, giving virtually no importance to its average choice, which was established assuming a slightly worse scenario than was described for a European population of 5 events per 100 patient-days (Allegranzi, 2011).

4. Analyses set

Study protocol mentioned that analysis will be done considering the intention to treat principle. However, during study conduction, some randomized patients did not require simultaneous insertion of all three devices (ETT, CVC and UC) due to illness severity, or the attending physician decided not to insert the devices. Those cases were excluded from the analyses. Consequently, main analysis will be carried out considering a Per Protocol Set (PPS) above. Our expectations are that per protocol and full compliance sets will be the same. Nevertheless, if it happens otherwise, full compliance set must be used to evaluate efficacy measures (infection incidences) and per protocol set to evaluate security measures (adverse events).

4.1) Per Protocol Set

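### As written, the SAP leaves central adjudicators unmasked to arm, which exposes the exploratory coated-versus-habitual risk ratios to detection bias that record redaction could reduce

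*SAP*

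**What the plan says.** Section 3.1 describes the trial as "Pilot exploratory, randomized, open label, controlled trial". Section 3.2 closes with "Due to technical reasons, there will be no blinding"; the technical reasons are not explained and no group of people is exempted.

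Section 3.3 sends every event to one place: "All events will be adjudicated by the coordinating center". It also gives adjudication a classification task: "Sepsis will be further classified as probably related to devices or non-related to the devices after adjudication". Some criteria in the same section call for judgement:

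- VAP requires "New or progressive radiographic consolidation or infiltrate".
- CAUTI requires "The attending physician believes there is an acute infection and prescribes antibiotics" and also "There is no other plausible source of infection at the time the diagnosis of CAUTI is made".
- CRBSI requires that the pathogen is not explained by infection elsewhere.

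Investigation of a possible event starts when a site introduces a new antibiotic class.

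Section 5.3, headed as exploratory, compares coated with habitual devices by risk ratio. It reports both adjudicated and centre-reported events without saying which is the main version, and bases simulations for a larger trial on these models. The SAP says nothing about masked review, redacted records or adjudicators independent of the trial team.

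**The concern.** Central adjudication in an open-label trial is normally there to put some distance between knowledge of the treatment and the classification of outcomes. It does this only if the readers do not know the arm. Here the stated rule is that nobody is blinded.

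Device-relatedness is the most exposed item, because the randomised treatment is the device itself. A reader who knows that a catheter was coated has a reason, conscious or not, to favour another source. The same pull applies to a borderline radiograph or to the plausibility of another source of infection.

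At stake is the arm contrast. Occurrence of sepsis by arm, the combined infection endpoint and the individual infections are secondary objectives in section 2.1, and section 5.3 carries the fitted models into planning for a larger trial. A contrast tilted by classification would make those scenarios look better or worse than they should.

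**Working it through.** **1. The two rules side by side.** Section 3.2 has no blinding and no exception. Section 3.3 has all events adjudicated centrally and is silent on masking. With nothing else in the SAP, the general rule governs the adjudicators. The obstacle in 3.2 is technical, which plausibly refers to staff who insert and handle the devices. Central review uses temperature, white cell count, cultures, images and SOFA, and none of these requires knowing whether a device was coated.

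**2. Which items depend on a central reader's judgement.**

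| Item | Exposure at central review |
|---|---|
| Sepsis related or unrelated to devices | Judgement, limited by the 48-hour rule and an open list of unrelated sources |
| VAP infiltrate | Image reading |
| CRBSI, pathogen not from another site | Judgement |
| CAUTI, no other plausible source | Judgement |
| CAUTI, attending physician's belief and prescription | Decided at the site; redaction does not help |
| Purulent secretions | Observed at the bedside; central reader sees the record |
| SOFA rise, urine count, matched cultures, time to positivity | Largely objective |

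**3. Size, by illustration only.** The SAP has no figure to reproduce on this point and gives no event counts. Suppose the true risk ratio is 1, time at risk is equal, and a share q of true events is rejected at adjudication. Then

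observed RR = (1 − q_coated) / (1 − q_control).

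The rejection shares below are assumptions:

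| q coated | q control | Observed RR |
|---|---|---|
| 10% | 10% | 0.90/0.90 = 1.00 |
| 10% | 5% | 0.90/0.95 = 0.95 |
| 20% | 10% | 0.80/0.90 = 0.89 |
| 20% | 5% | 0.80/0.95 = 0.84 |
| 30% | 10% | 0.70/0.90 = 0.78 |

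**4. Against sampling error.** Section 3.4 gives 100 patients, a prior centre of 8 events per 100 patient-days and a European figure of 5. It gives no patient-days. If its 3 per 100 patient-days is read as the overall interval length L, the normal approximation T = r(2 × 1.96/L)² gives

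- r = 0.05: T ≈ 854 patient-days, about 8.5 per patient;
- r = 0.08: T ≈ 1,366 patient-days, about 13.7 per patient.

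With 50 patients per arm, sepsis events per arm are 0.05 × 50 × 8.5 = 21.25, or 0.08 × 50 × 13.7 = 54.8. The 95% interval around RR = 1 is exp(±1.96 √(2/events)):

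- 21.25 events: about 0.55 to 1.82;
- 54.8 events: about 0.69 to 1.45.

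Every ratio in step 3 lies inside both intervals.

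**5. The pooled primary incidence.** Take 8 true events per 100 patient-days, split equally between arms. Rejecting 10% in both arms leaves 8 × 0.90 = 7.2. Rejecting 20% and 10% leaves 8 × (0.80 + 0.90)/2 = 6.8. The shift is 0.4 per 100 patient-days, against an interval length of about 3.

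**The case against.** The strongest reply is that the no-blinding sentence sits in the section on randomisation and concealment, straight after a statement about the investigator, and so reads naturally as a statement about treatment. Adjudication procedure is often left to a protocol or charter, and neither is shown. This stands in part: a reader might infer that adjudicators actually worked unmasked, and the SAP does not establish that. What it does establish is an unqualified rule. A charter that provided masking would conflict with it, and the sentence would still need correcting.

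Second, the centre-reported version of sepsis is rule-based (a SOFA rise plus new antibiotic use) and involves no adjudicator opinion. So it would be too strong to call adjudication the only safeguard. The check is partial, however, because prescribing at the sites is also unblinded.

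Third, many criteria are objective, and section 5 specifies no arm comparison of the device-related subclass as such. That narrows the exposure but does not remove it.

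Fourth, masking would protect only the central step. This is correct; masked adjudication should not be presented as removing detection bias from this trial.

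Fifth, a small assumed event count can make the bias look large. With 21.25 events per arm, reclassifying one to three coated-arm events gives 20.25/21.25 = 0.95 to 18.25/21.25 = 0.86. With 54.8 it gives 53.8/54.8 = 0.98 to 51.8/54.8 = 0.95. Individual infections may be rarer, but the SAP gives no counts for them.

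**Conclusion.** The point holds in a limited form. As written, the SAP leaves adjudicators unmasked to arm, and the reason it gives need not extend to central record review. The exposure falls mainly on the exploratory risk ratios in section 5.3 and the simulations that use them.

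A reader might infer that the primary result is compromised. The documents do not support that: sections 3.4 and 5.2 estimate an incidence from an intercept model, feasibility is assessed by recruitment and site input, and a classification shift that differs by arm is diluted in the pooled rate.

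The size of any bias cannot be estimated from the SAP. On the assumed rejection shares it runs from none to a risk ratio of 0.78 when the truth is 1, within this pilot's sampling error. Wide intervals do not remove the bias from the centre of the estimates passed to the simulations. The conclusion assumes that no unseen document overrides section 3.2. This is a worthwhile low-burden improvement to an exploratory pilot, not a fatal flaw.

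**What to change.** - In section 3.2, limit the no-blinding sentence to treatment and bedside staff.
- In section 3.3, state that adjudicators receive records with arm, device brand and coating removed, and classify events without knowledge of allocation.
- In section 5.3, name the masked adjudicated events as the main version for the arm comparison, with centre-reported events as sensitivity.
- Section 4 shows that the SAP was written once the trial was under way, so some events may already have been adjudicated. Any that were read with the arm known should be re-read by an existing coordinating-centre reader who has not seen them. The same reader cannot reliably be masked a second time. Where no such reader exists, flag the events and report this as a limitation of the arm comparison.

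The cost is a redaction step and some re-reading in a 100-patient trial, with no additional adjudicators. The SAP gives no cost information, so calling this low-burden is a judgement. The antibiotic trigger and the attending physician's part of the CAUTI definition stay unmasked and should be acknowledged when the risk ratios are reported.

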All patients that were randomized, fulfill all inclusion and exclusion criteria, and receive the three devices (ETT, CVC and UC) from allocated arm (coated or habitual) at least one time.

4.2) Full compliance set

All patients that were randomized, fulfill all inclusion and exclusion criteria, and receive the three devices (ETT, CVC and UC) from allocated arm (coated or habitual) all the times that were needed.

5. Analyses Methods

Continuous data will be reported as mean (standard deviation) or median (quartiles) as appropriate. Categorical variables will be described by absolute and relative frequencies.

5.1) Baseline characteristics

Patients' baseline characteristics will be presented without any hypothesis test comparing patients allocated to Coated versus Habitual devices.

5.2) Primary outcome

As described at section 3.4 (sample size), the primary outcome of incidence of sepsis, will be estimated via Bayesian *Poisson* regression model with intercept parameter assuming non-informative normal prior centered in 8 event per 100 patient-day incidence rate, $N(e^{0.08}, 5)$.

5.3) Exploratory outcomes

The same Bayesian *Poisson* regression model with intercept parameter assuming non-informative normal prior centered in 8 event per 100 patient-day incidence rate, $N(e^{0.08}, 5)$, will be done to estimate other infection incidences (VAP, CRBSI, CAUTI).

Besides, the same model will be used to compare patients that used coated devices versus habitual devices. Results will be reported as Risk Ratios (RR) with 95% Credible Intervals. Models will be adjusted for admission type, baseline SOFA and the stratification variable (presence of sepsis at randomization).

Results will be reported considering adjudicated events and events reported by the centers. Sepsis, as reported by centers will be considered as: two point increase in SOFA plus newest use of ATB. The end of sepsis will be considered at the time of ATB withdrawal concomitant with any improvement in SOFA.

Based on those models, we will run simulations to explore scenarios for a larger trial.

5.4) SOFA

We intent to evaluate SOFA during ICU stay using hierarchical Bayesian linear regression models assuming intercept and slope hierarchical effects to patient to include individual time dependence, adjusted for baseline SOFA, and interaction of time and allocated device (coated or habitual). All priors shall be non-informative Normal distributed.

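### Section 4 replaces intention to treat with sets defined by device receipt after open-label randomisation and plans no all-randomised comparison of the arms

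*SAP*

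**What the plan says.** Section 4 of the SAP records the protocol's principle: "Study protocol mentioned that analysis will be done considering the intention to treat principle". It then gives two reasons why randomised patients fell out during the trial. The first is clinical need: "some randomized patients did not require simultaneous insertion of all three devices (ETT, CVC and UC) due to illness severity". The second is a choice: "or the attending physician decided not to insert the devices". The consequence is "Those cases were excluded from the analyses. Consequently, main analysis will be carried out considering a Per Protocol Set (PPS) above".

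Two sets follow. The per-protocol set (4.1) keeps eligible randomised patients who "receive the three devices (ETT, CVC and UC) from allocated arm (coated or habitual) at least one time". The full compliance set (4.2) keeps those who "receive the three devices (ETT, CVC and UC) from allocated arm (coated or habitual) all the times that were needed". Section 4 states "Our expectations are that per protocol and full compliance sets will be the same", but adds that "if it happens otherwise, full compliance set must be used to evaluate efficacy measures (infection incidences) and per protocol set to evaluate security measures".

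Other sections bear on this:
- 3.1 and 3.2 describe 1:1 randomisation, open label, of patients who will need the three devices. The arm is disclosed once the patient is registered.
- 5.3 compares the arms with Poisson models adjusted for admission type, baseline SOFA and sepsis at randomisation, then uses those models to simulate a larger trial.
- 5.6 tests adverse events between the study groups and names no analysis set.
- No section defines an all-randomised set, even for a sensitivity analysis.

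**The concern.** Both sets are defined by what happened after the arm was known. The two reasons for exclusion are not equally serious. Patients who turned out not to need the devices lie outside the population in 3.1, and leaving them out biases the comparison only if judged need depended on the arm. A physician's decision not to insert can depend on the arm directly. Full compliance goes further: it depends on every replacement during follow-up, so patients who need more replacements have more chances to be removed.

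Three things are at stake.
- The coated-versus-habitual ratios are exploratory, but they are inputs to the simulations for the next trial, and no all-randomised result is planned to set beside them.
- The set used for the primary incidence in 5.2 depends on whether compliance proves complete. The question in 2.1 concerns patients who require the three devices, not those who received the allocated type every time.
- Section 4 places adverse events in the per-protocol set. That omits patients exposed to only one or two allocated devices, or to an other-arm device in place of an allocated one. A patient who received all three and later an other-arm replacement stays in.

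**Working it through.** **1. The plan's own precision figure (SAP 3.4).** I read the 3 overall and 4 per group as widths of 95% intervals per 100 patient-days, at the rate of 8 on which the prior is said to be centred. The SAP does not give patient-days per patient, so these are solved for.

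Width = 2 × 1.96 × √(rate/T), so T = rate × (3.92/width)².
- Overall: 0.08 × (3.92/0.03)² = 1,366 patient-days, or 13.7 per patient for 100 patients; 683 per arm and 54.63 events per arm.
- Per group: 0.08 × (3.92/0.04)² = 768 patient-days, or 15.4 per patient for 50 patients; 61.5 events.

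The two figures agree with each other at about 14 to 15 days per patient and are not in dispute. They give the scale of chance variation in a ratio with no true effect, exp(±1.96 × √(2/events)):
- 54.63 events per arm: 0.69 to 1.45
- 61.5 events per arm: 0.70 to 1.42

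**2. Shift in the arm ratio from unequal exclusion (assumed inputs, no true effect, unadjusted).** Let x be the share of an arm's patient-days excluded (x1 and x0 for the two arms) and k the rate in the excluded relative to the arm average.

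Ratio = [(1 − x1·k)/(1 − x1)] ÷ [(1 − x0·k)/(1 − x0)]

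| x1, x0 | k = 0.5 | k = 2 |
|---|---|---|
| 0.10, 0.10 | 1.00 | 1.00 |
| 0.10, 0.05 | 1.03 | 0.94 |
| 0.05, 0 | 1.03 | 0.95 |
| 0.10, 0 | 1.06 | 0.89 |

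For example, with x1 = 0.10, x0 = 0 and k = 2: (1 − 0.20)/0.90 = 0.89. Equal exclusion of similar patients does no harm; exclusion that differs by arm does.

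**3. Shift in the 5.2 incidence if it moves to the full compliance set.** Rate = 8 × (1 − x·k)/(1 − x), for an assumed share x dropped.
- x = 0.05: 8.2 (k = 0.5) or 7.6 (k = 2)
- x = 0.10: 8.4 or 7.1

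The planned half-width is 3/2 = 1.5.

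**4. Dependence of compliance on follow-up.** If each replacement has an assumed chance q of being off-arm, a patient needing three stays in the set with probability (1 − q)³: 0.86 for q = 0.05 and 0.73 for q = 0.10. A patient needing none stays with probability 1.00.

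**5. Adverse events missed.** If n exposed patients are left out and the event risk is p, the chance of missing at least one event is 1 − (1 − p)^n.

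| n | p = 2% | p = 5% | p = 10% |
|---|---|---|---|
| 2 | 4% | 10% | 19% |
| 5 | 10% | 23% | 41% |

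Both n and p are assumed.

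**The case against.** The strongest reply has four parts.

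- **The trial is an exploratory pilot.** Its main outcomes are feasibility and pooled incidence, and 2.1 and 3.1 concern patients who need all three devices. This stands for the pooled incidence, which may stay restricted to such patients. It does not protect a comparison of arms.
- **The 5.3 models adjust for baseline SOFA, admission type and sepsis at randomisation.** Illness severity is a stated reason for exclusion, so this is relevant and may absorb part of the selection; the ratios above ignore it. It cannot remove selection on factors not measured at baseline, or on what happens later.
- **Nothing shows that harm occurred.** Every exclusion share is assumed, the shifts lie inside pilot noise, and the SAP expects the two sets to coincide. This is true. But the credible interval shows imprecision and does not show selection.
- **An all-randomised run is not straightforward for VAP, CRBSI and CAUTI.** A patient who never had the device has no evident time at risk, and the 3.3 rule on device-related sepsis is timed from insertion. This stands, and simply rerunning every 5.3 model on all randomised patients would leave it unresolved.

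A reader might also infer that sections 4 and 5.6 contradict each other on the adverse-event population. They do not: section 4 assigns adverse events to the per-protocol set, and the word all in 5.6 qualifies the events, not the patients. What remains is a poor choice of safety population.

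**Conclusion.** The point holds and should be fixed. The text itself establishes that sets defined by device receipt replace intention to treat, that infection incidences move to a compliance-dependent set if the two sets differ, and that no all-randomised comparison is planned. The protocol's intention-to-treat wording is known only through section 4.

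A reader might go further and infer that the coated-versus-habitual ratio is biased in a known direction or by a material amount. The SAP does not support that. It gives no exclusion counts by arm, and the illustrated shifts of 0.89 to 1.06 rest on assumed shares and rates, before adjustment. They are small beside a chance range of about 0.69 to 1.45, which itself rests on reading the 3.4 figures as interval widths. The illustrated 5.2 shifts, from 8 to between 7.1 and 8.4, are likewise inside the planned half-width of 1.5. The case for change is that the safeguard is cheap and the ratios will be used to plan a larger trial.

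**What to change.** 1. Run the coated-versus-habitual comparison on all randomised patients by allocated arm for outcomes that need no device to be defined: any sepsis from 48 hours after randomisation, mortality and SOFA. Use the follow-up available and state how much is missing by arm. Word 5.3 by allocation rather than use.
2. For VAP, CRBSI and CAUTI, choose one basis and state it: either all ICU patient-days after randomisation by allocated arm, or patients with that device inserted, analysed by allocated arm and labelled as a subset analysis.
3. Keep the per-protocol and full compliance sets as labelled sensitivity analyses. The 5.2 incidence may stay restricted to patients who required all three devices, but should not move to the full compliance set.
4. Analyse adverse events in all randomised patients with at least one study device inserted, by allocated arm, and say so in both section 4 and 5.6.
5. Report exclusions from each set by arm and reason.

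The cost is SAP wording, a decision on the denominator for the device infections, and further runs of the planned models. Follow-up may be incomplete in patients already excluded. The all-randomised ratio is somewhat diluted: if a share x of patient-days, at average risk, had no device benefit, an assumed true ratio of 0.70 becomes (1 − x) × 0.70 + x, which is 0.715 for x = 0.05 and 0.73 for x = 0.10. The per-protocol estimate remains alongside.

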CRITIC

Pilot study

Coated devices to decRease InfecTion in the ICu Statistical Analysis Plan

Chief Investigators:

[name], PhD

[name], PhD

Statistician

[name] [name]

Sponsor:

Bactiguard AB, Tullinge, Sweden

Sponsor representative:

[name], PhD

Research Institute, HCor - Hospital do Coração, São Paulo, Brazil

SUMMARY

| | |
|---|----|
| 1. Administrative information..... | 4 |
| 2. Aim and objectives | 5 |
| 2.1) Objectives..... | 5 |
| 3. Study methods | 6 |
| 3.1) Trial design | 6 |
| 3.2) Method of randomization and concealment allocation | 6 |
| 3.3) Outcomes | 6 |
| 3.4) Sample size..... | 8 |
| 4. Analyses set..... | 9 |
| 4.1) Per Protocol Set..... | 9 |
| 4.2) Full compliance set..... | 9 |
| 5. Analyses Methods | 9 |
| 5.1) Baseline characteristics..... | 9 |
| 5.2) Primary outcome..... | 10 |
| 5.3) Exploratory outcomes | 10 |
| 5.4) SOFA | 10 |
| 5.5) Subgroup analysis..... | 11 |
| 5.6) Safety and Adverse Events..... | 11 |
| 5.7) Missing data and imputation | 11 |
| 6. Statistical software | 12 |
| REFERENCES | 13 |

ABBREVIATIONS

| | |
|-------|--|
| AE | adverse event |
| ATB | antibiotics |
| CAUTI | catheter related urinary infection |
| CRBSI | catheter related bloodstream infection |
| CVC | central venous catheters |
| ICU | intensive care unit |
| ETT | endotracheal tubes |
| UC | urinary foley catheters |
| RR | risk ratio |
| SAP | statistical analysis plan |
| SOFA | sequential organ failure assessment |
| VAP | ventilator associated pneumonia |

1. Administrative information

Statistical Analysis Plan (SAP) for the CRITIC Pilot Study (Coated devices to decrease Infection in the ICU).

- ClinicalTrials.org Registration: NCT03868241
- Protocol Version 2.0 – January, 2019.
- SAP Revision:

| SAP version | Protocol Version | Description and Reason for Change | Date |
|--------------------|-------------------------|--|-------------|
| 1.0 | 2.0 | Not Applicable | 03/10/2019 |

2. Aim and objectives

The full rationale for undertaken the trial is explained in detail in the Protocol. Briefly, CRITIC is a pilot study to assess feasibility and potential recruitment rate for a larger trial using coated (Bactiguard®) devices in critically ill patients. And establish the incidence of ICU-acquired sepsis in the most severe critically ill patients in Brazil.

2.1) Objectives

Primary objectives:

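### The sepsis-incidence interval in SAP 5.2 and the lengths in 3.4 hold for the participating ICUs only; for the wider Brazilian aim in section 2 they leave out between-ICU variation, and 5.3 omits site as a stratification factor.

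*SAP*

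**What the plan says.** Section 2 (Aim and objectives) states that the pilot will, besides assessing feasibility, "establish the incidence of ICU-acquired sepsis in the most severe critically ill patients in Brazil". The formal primary objective in 2.1 is narrower: of the patients who need all three devices, how many develop sepsis "from 48 hours after randomization until day 28 after randomization or until ICU discharge".

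The trial has several sites. Section 3.2 says that randomisation "will be done in blocks stratified by site and by the presence of sepsis at randomization", and section 3.3 says "We expect a recruitment rate of approximately 1.3 patients a month per site". The number of sites is not given.

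Section 3.4 begins "This is a pilot study including 100 unique patients", defines incidence density as events divided by total patient-days at risk, and says that the sample will "inform 95% credible intervals with approximately 3 events per 100 patient-days overall", with 4 per group. Its reference point for the assumed rate of 8 is "a slightly worse scenario than was described for a European population of 5 events per 100 patient-days".

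Section 5.2 then fixes the analysis: "the primary outcome of incidence of sepsis, will be estimated via Bayesian *Poisson* regression model with intercept parameter", with a vague normal prior. Section 5.3 adapts this model to compare the groups, adjusting for admission type, baseline SOFA and sepsis at randomisation. It describes the last as the stratification variable, in the singular, and does not mention site. It also bases simulations for a larger trial on these models. The only hierarchical effects in the SAP are the patient-level ones in the SOFA model (5.4).

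**The concern.** A pooled Poisson model with a single rate treats every patient-day as exchangeable, whichever ICU it comes from. Its interval reflects how many events happen to occur in the ICUs that took part. It does not reflect the fact that another set of ICUs might have had a different underlying rate. If the result is read as the incidence in Brazil, as section 2 invites, that second source of uncertainty is missing from both the interval in 5.2 and the planned precision in 3.4.

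Sepsis incidence is one of the two main outcomes and the only one with a stated model and precision. Simulations built on a model without a site component would also pass no between-site variation to the larger trial. A smaller inconsistency is that 3.2 names two stratification factors and 5.3 carries only one forward.

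**Working it through.** **Inputs from the SAP.** 100 patients (3.4); rates of 5 and 8 per 100 patient-days (3.4); a 95% interval of about 3 per 100 overall and 4 per group (3.4), both read as interval lengths per 100 patient-days; a risk window from 48 hours to day 28, so at most 26 days (2.1).

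**Assumed, because the SAP does not give them.** Number of sites K = 6, 10 or 20. At 1.3 patients per site per month, 100/1.3 = 77 site-months, or 12.8, 7.7 and 3.8 months of recruitment. Between-site SD of the log rate s = 0 to 0.5. For scale, the median rate ratio between two sites is exp(0.954 × s), which is 1.15, 1.33 and 1.61 for s = 0.15, 0.3 and 0.5.

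**Step 1: reproduce the stated precision.** The SAP gives no total patient-days T, so T has to be back-solved. With a gamma interval on y = rate × T events:

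| Rate per 100 | T for length 3.0 | Events | Length with T/2 (per group) |
|---|---|---|---|
| 5 | 850 | 43 | 4.2 |
| 8 | 1,364 | 109 | 4.2 |

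The 3-and-4 pair is the √2 ratio of a plain Poisson model (3.0 × 1.414 = 4.2), so it contains no between-ICU component. The prior does not supply one either: with 109 events in 1,366 patient-days the interval is 6.56 to 9.56 with the prior mean as printed, e^0.08, and 6.55 to 9.55 with log 0.08.

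The row for 8 per 100 is possible only if repeat episodes count. It needs 109 events in 100 patients. If only first episodes count, expected time at risk cannot exceed (1 − exp(−0.08 × 26))/0.08 = 10.9 days per patient, against the 13.6 required. The main figures below therefore use 5 per 100.

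**Step 2: add between-ICU variation.** With equal patient-days per site,

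Var = rate/T + (CV × rate)²/K, where CV² = exp(s²) − 1.

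At rate 0.05, T = 850 and s = 0.3: CV = 0.307; rate/T = 5.88 × 10⁻⁵; (0.307 × 0.05)² = 2.35 × 10⁻⁴. The inflation factor is f = √(Var ÷ (rate/T)), the length needed is 3.0 × f, and the coverage of the plain interval is 2Φ(1.96/f) − 1.

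| K | Between-site part | f | Length needed | Coverage of plain interval |
|---|---|---|---|---|
| 6 | 3.92 × 10⁻⁵ | 1.29 | 3.9 | 87.1% |
| 10 | 2.35 × 10⁻⁵ | 1.18 | 3.5 | 90.2% |
| 20 | 1.18 × 10⁻⁵ | 1.10 | 3.3 | 92.6% |

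Simulation with patients assigned at random to sites agrees: about 87/90/92%.

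**Step 3: vary the assumptions.** Simulated coverage of the population rate at 5 per 100, K = 6/10/20, all episodes counted: s = 0, about 95% throughout; s = 0.15, about 92 to 94%; s = 0.5, about 74/79/86%. Counting first episodes only gives 87/90/92% at s = 0.3. At 8 per 100 with repeat episodes and s = 0.3 it is about 75/81/87%.

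**Step 4: the other target.** Coverage of the participating ICUs' own pooled rate is 94 to 96% in every setting.

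**Step 5: the group comparison.** If site k has rate r_k in one arm and θ × r_k in the other, with T_k/2 patient-days in each, the pooled ratio is θ × Σ r_k T_k / Σ r_k T_k = θ. Site cancels when arms are balanced within site, which stratified randomisation makes approximately true. Balance will not be exact: 20 sites by 2 sepsis strata would leave 100/40 = 2.5 patients per stratum.

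**The case against.** The strongest reply is that the SAP's working target is the enrolled cohort. The reference to Brazil occurs in a brief summary of the aim. The formal objective in 2.1 and the definition in 3.4 both describe the pooled rate among the patients studied, and for that rate the plain model is correct. This stands. A reader might infer that the primary model is wrong and must be replaced by a hierarchical one; the SAP does not support that. Nor does 5.2 say that the intercept is the only term. That is inferred from the absence of any other term and from the precision reproduced in Step 1.

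A reader might also take the lowest coverage figures as the expected loss. They need few sites, a large SD, or a rate of 8 with repeat episodes counted. The SAP does not show that ICUs differ at all. The 5 and 8 per 100 in 3.4 refer to different populations and do not estimate a between-site SD.

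A third reply is that a site term on about 43 events depends heavily on its prior, and that it cannot turn the participating sites into a representative sample of Brazilian ICUs. Both points stand, and they are why the site model belongs beside the primary analysis and not in its place.

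Finally, a reader might infer that leaving site out of 5.3 invalidates the comparison of devices. Step 5 shows why it does not.

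What none of this answers is that section 2 states a wider aim than the interval can serve, and that nothing in 3.4 or 5.2 tells the reader so.

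**Conclusion.** The point holds as a mismatch between the stated aim and what the interval measures. The planned interval is valid for the rate in the participating ICUs. Read as an interval for a wider population of ICUs, it is too narrow if ICUs differ: about 87/90/92% coverage where 95% is claimed, at 5 per 100, an assumed SD of 0.3 and 6/10/20 sites, and no loss if they do not differ. The direction follows from the model. The size rests entirely on the assumed number of sites and SD, and on treating the sites as draws from a wider population. The omission of site in 5.3 is a real but minor inconsistency with 3.2, and little change in the rate-ratio interval should be expected from correcting it.

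**What to change.** 1. **5.2:** keep the plain Poisson model as primary and label its estimate and interval as the rate in the participating ICUs.
2. **3.4:** state that the lengths of about 3 and 4 per 100 patient-days apply to those ICUs and contain no between-ICU variation.
3. **Supplementary analysis:** add a Poisson model with a site random intercept, a stated weakly informative prior on the site SD (for example half-normal with scale 0.5) and a second prior scale. Report the incidence averaged over sites, exp(μ + SD²/2), and not exp(μ).
4. **Larger-trial simulations in 5.3:** carry in a range of between-site SD.
5. **5.3 models:** name site as the second stratification factor and include it as a random intercept.

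The cost is some wording and a few lines of Stan; site is already recorded as a randomisation stratum, and 5.4 already plans hierarchical models. The drawback is a wider, prior-dependent supplementary interval. At 5 per 100, SD 0.3 and prior scale 0.5, its median length is 4.8/4.0/3.6 with 6/10/20 sites, with coverage of 96 to 97%. With no site differences it is still 4.2/3.7/3.4, against 3.0 for the plain model. At SD 0.3, prior scales of 0.25/0.5/1 give 3.7/4.8/6.5 with 6 sites and 3.3/3.6/3.9 with 20. The report should say that this analysis does not make the sites representative of Brazil.
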